#### 4.2. Outcome

The main outcome measure is an improvement in the validated Voice Handicap Index self-assessment score following up to six sessions of therapy by an authorised CVT-P in patients with MTD ([Appendix 1](#))

Secondary outcome measures include:

- 1) A questionnaire to evaluate the acceptability of the approach to patients ([Appendix 2](#))
- 2) A questionnaire to evaluate the perceived effectiveness of the therapy from the Therapist's perspective. ([Appendix 3](#))
- 3) Qualitative comparison of the specific techniques used by the CVT-P based on a log of techniques used during the therapy session ([Appendix 4](#)) and qualitative assessment of anonymised, redacted transcripts of therapy sessions in those who have given additional consent
- 4) Comparison of pre- and post-treatment results of:
  - a. a range of simultaneously acquired acoustic and EGG measures made on voice recordings of continuous speech, phrases based on phonetically selected texts and sustained vowels ([Appendix B](#))

- b. psychoacoustic evaluation of the recorded voice samples using the CAPE-V ([Appendix 5](#)) and CVT derived assessment tools ([Appendix 6](#))
  - c. vocal tract discomfort scale – a self-reported rating scale ([Appendix 7](#))
  - d. change in the aerodynamic measure, the Maximum Phonation Time (MPT) ([Appendix 8](#))
- 5) Review of qualitative and quantitative results with recommendations on the feasibility and design of performing a larger RCT. The results will be published in a peer reviewed publication

## 5. STUDY DESIGN AND METHODS OF DATA COLLECTION AND STATISTICAL ANALYSIS PLAN

The aim of this proof-of-concept study is to evaluate whether the approach used in the Complete Vocal Technique to improve voice production in singers and performers can be applied to patients with Type I-III Muscle Tension Dysphonia pattern using a Telehealth medium. Ten consecutive patients seen in an NHS Joint SLT/ENT Voice clinic who meet the inclusion/exclusion criteria and who give consent will be invited to take part in the study. In addition, MTD patients awaiting SLT-VT will be invited to take part in the study. Data including validated patient self-assessment questionnaires, audio-perceptual evaluation of the voice, acoustic and EGG recordings of the voice and an aerodynamic measure (MPT), will be collected after recruitment in a research clinic at the beginning of the study (t=0) and again at the end of the study (t=8). Data will be collected by the study Laryngologist or study SLT. Additional questionnaires will also be given to patients and Therapists at the end of the study to obtain feedback on satisfaction with achievement of goals, the therapy, and the use of Teletherapy to deliver the treatment. Quantitative standard descriptive and inferential statistics methods will be applied to compare pre-and post-therapy measures using the VHI as the primary outcome measure as well as the selected secondary outcome measures.

### VHI

Paired-samples t tests will be applied to the pre-treatment and post-treatment primary outcome measure scores (total VHI score).

### Acoustic, EGG and MPT measures

Paired-samples t tests will also be applied to the secondary acoustic outcome measures (EGG, acoustic and MPT measures), together with 95% confidence intervals.

To control for Type 1 error of the primary outcome and secondary outcome analyses while maintaining an acceptable level of statistical power, the alpha level for all t-test comparisons will also be assessed at .025. Treatment effects will be assessed by comparing the pre-treatment to post-treatment change ( $\Delta$ ) scores, plotted as a forest plot in order to display the average  $\Delta$  change for each outcome measure and corresponding 95% confidence interval. Any significant treatment effects will be followed up with calculations of effect size using Cohen's d.

SHORT TITLE/ACRONYM: CVT4MTD

IRAS:306954

Measurement reliability for acoustic analyses will be calculated by reanalysis of 10% of the recordings. The recordings chosen for reliability analysis will be randomly selected from the total number of recordings. Pearson product–moment correlations will be used to assess inter-measurer and intra-measurer reliability of the acoustic and EGG measurements.

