### **CAPE-V**

For the secondary outcome measure CAPE-V, three experienced judges will be asked to rate all voice samples using the first four dimensions (overall severity, roughness, breathiness, and strain; on 100-mm visual analog scales (VAS) (Kempster et al, 2009). The judges will be blinded to pre- and post-treatment status of the voice samples. The voice samples will be presented in random order. The rating forms will be scored, and then scores for each subject will be averaged across the three judges. Average scores will be used for group analyses. Interrater agreement will be assessed using procedures described by Kreiman and Gerratt (1998). Agreement equivalent to within 1 point on a 7-point Equal Appearing Interval (EAI) scale will be calculated for each possible pair of raters for each voice sample. On a 100-mm visual analog scale, scores that fall within 7.2 mm will be considered to be in exact agreement on a 7-point EAI, and scores that are within 21.5 mm (7.2 + 14.3 mm) will be considered to be within 1 scale value. Two scores will be considered to agree if they fall within  $\pm 21.5$  mm on the VAS (probability of chance agreement  $p = 0.39$ ). The probability of agreement will be calculated by totaling all pairs of scores that agree and dividing by the total number of score pairs. Twenty percent of the voice samples will be randomly selected to be repeated for each judge. Repeat ratings will be used to assess intra-rater agreement, using the same calculation. To test for differences in the four CAPE-V dimensions, a multivariate analysis of variance will be applied to the pre-treatment to post-treatment change ( $\Delta$ ). Paired-samples  $t$  tests will also be applied to pre-treatment to post-treatment changes for each of the four dimensions within each group. A multiple comparison adjustment will be made for the four comparisons using the Bonferroni multiple-comparison procedure. The confidence intervals will be similarly adjusted for four comparisons, so the reported 95% confidence interval (CI) will actually be a 98.75% CI, which is a Bonferroni-adjusted CI.

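### Testing each outcome at .025 does not control Type 1 error across the primary and secondary analyses, and Cohen's d is planned only for significant results

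*Combined protocol and SAP*

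**What the plan says.** All the relevant text is in Section 5 of the combined protocol and SAP unless stated otherwise.

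- **Level and purpose** (Acoustic, EGG and MPT measures): "the alpha level for all t-test comparisons will also be assessed at .025". The stated purpose is "To control for Type 1 error of the primary outcome and secondary outcome analyses while maintaining an acceptable level of statistical power". No familywise target, number of tests, ordering of tests or sidedness is given.
- **Tests at that level:** paired t-tests are planned for total VHI (VHI), for the acoustic, EGG and MPT measures, and for the VTD frequency and severity totals (Other Questionnaires). Section 4.2 describes the acoustic and EGG set as "a range of simultaneously acquired acoustic and EGG measures", so it is not limited to one of each.
- **CAPE-V** has its own rule: "A multiple comparison adjustment will be made for the four comparisons using the Bonferroni multiple-comparison procedure", and "the reported 95% confidence interval (CI) will actually be a 98.75% CI, which is a Bonferroni-adjusted CI".
- **Individual VTD items** are compared by Mann-Whitney and ANOVA (Other Questionnaires), with no stated level.
- **Display:** a forest plot shows the average "change for each outcome measure and corresponding 95% confidence interval".
- **Effect sizes:** "Any significant treatment effects will be followed up with calculations of effect size", using Cohen's d. None is planned for the other outcomes.
- **Purpose of the sample size** (Section 7.2.1): ten patients, chosen arbitrarily, to supply what a later power analysis needs.

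**The concern.** A per-test level of .025 controls the error of each test. It does not control the error of a set of six or more, and the plan says that it serves the primary and secondary analyses together. A report that followed this text could present a secondary result with p below .025 as error-controlled when it is not. The rule also covers only t-tests, so the item-level VTD comparisons, which are secondary analyses too, fall outside it.

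The second issue is selection. If d is calculated only after a significant test, the printed values are those that happened to be large. That matters more than usual here because the study exists to inform the sizing of a later one.

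Two smaller gaps follow from the same paragraph. On a two-sided reading, tests at .025 do not match the plotted 95% intervals, which are not labelled unadjusted. And the word covering all t-tests does not exempt CAPE-V, although CAPE-V has a different rule.

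**Working it through.** **1. What .025 covers.** The plan gives no derivation of .025. The nearest derived figure is the CAPE-V interval, which reproduces as 1 − 0.05/4 = 0.9875, so the base there is 5%. On that base 0.05/2 = 0.025, a split over two tests: 1 − 0.975² = 0.049.

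**2. Count of t-tests with no other adjustment.** VHI 1 + MPT 1 + acoustic at least 1 + EGG at least 1 + VTD totals 2 = at least 6. CAPE-V is left out because it has its own correction.

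**3. Familywise error if the tests are independent.**

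| Set of tests | Formula | Result |
|---|---|---|
| Six at .025 | 1 − 0.975⁶ | 14.1% |
| Five secondary only, at .025 | 1 − 0.975⁵ | 11.9% |
| Eight at .025 | 1 − 0.975⁸ | 18.3% |
| Six at .025 plus four CAPE-V at .0125 | 1 − 0.975⁶ × 0.9875⁴ | 18.3% |
| Six at .025 plus four CAPE-V at .00625 | 1 − 0.975⁶ × 0.99375⁴ | 16.2% |

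The CAPE-V level of .0125 is inferred from the 98.75% interval. The last row shows the result if .025 were the base instead (.025/4 = .00625). Bonferroni control at 5% over six tests would need 0.05/6 = 0.0083 per test.

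**4. Allowing for correlation.** The documents give no correlations, so these are assumed. Simulation used ten patients, two-sided paired t-tests, equally correlated normal changes and no true effect, with 200,000 runs.

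| Correlation | Six at .025 | Plus four CAPE-V at .0125 |
|---|---|---|
| 0.3 | 13.2% | 16.7% |
| 0.5 | 11.8% | 14.5% |
| 0.8 | 8.2% | 9.1% |

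**5. Test level against plotted interval.** With 9 degrees of freedom the two-sided critical t is 2.262 at .05, 2.685 at .025 and 3.111 at .0125. Dividing by √10 gives the smallest significant mean change/SD of change: 0.715, 0.849 and 0.984. A ratio between 0.715 and 0.849 therefore gives a 95% interval that excludes zero beside a test called non-significant.

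**6. Selection of Cohen's d.** Take d as mean change/SD of change, printed only if two-sided p < .025, with ten patients and 1,000,000 runs per value. The true values are assumed, since the documents give none.

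| True d | Share of studies printing d | Mean printed d | Mean d if always printed |
|---|---|---|---|
| 0.5 | 0.191 | 1.13 | 0.55 |
| 0.8 | 0.475 | 1.22 | 0.88 |
| 1.0 | 0.682 | 1.31 | 1.09 |

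If the threshold is 0.715 instead (one-sided .025, or two-sided .05), the mean printed d is still 1.01, 1.12 and 1.23.

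**7. What the forest plot preserves.** With ten patients, SD of change = half-width of the 95% interval × √10/2.262. The paired d can therefore be recovered for every outcome that is plotted.

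**The case against.** **On the error rate.** The plan claims no 5% familywise rate. It describes a compromise with power, and a stricter per-test level in a ten-patient proof-of-concept study can be read as partial mitigation. The 5% benchmark comes from the CAPE-V rule, which governs one family of four. Independence is also unlikely, since the acoustic and EGG signals are recorded together and the VTD totals come from one scale. Among the secondary tests alone the minimum count is five. Part of this stands: 14% is the independence end of a range that falls to about 8% for six tests. But six is a minimum count, none of the correlations examined brings the rate to 5%, and a compromise with no stated target cannot support a claim of control.

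**On the intervals.** Sidedness is not stated and the primary outcome is worded as an improvement. A one-sided .025 test matches a 95% interval, and the word also could mean that .025 is used in addition to .05. This stands as far as it goes: the mismatch depends on the two-sided reading. Neither alternative removes the multiplicity or the selection of d.

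**On Cohen's d.** The text does not forbid d for other outcomes, the forest plot allows recovery, and the investigators hold the full data. The planned next step is a randomised trial, for which a single-arm paired d is not in itself the effect size needed. So a biased future power analysis is possible but not shown. What remains is that the values printed as effect sizes would be selected for being large.

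**Conclusion.** The concern holds, as a minor one. The statement that .025 controls Type 1 error over the primary and secondary analyses is not supported: with the minimum of six t-tests the familywise error is 14% under independence and about 8% to 13% at assumed correlations of 0.8 to 0.3. It would be higher with more acoustic or EGG measures. The judgement against 5% rests on the base implied by the CAPE-V interval, because the plan states no target of its own. The single VHI test is not compromised.

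Tying d to significance inflates the printed values, to a mean of 1.13, 1.22 and 1.31 for assumed true values of 0.5, 0.8 and 1.0 on the two-sided reading. That d is planned for significant results only is inferred from the wording, but it is the natural reading. The damage is limited because the plotted mean changes and intervals keep the underlying information. The interval mismatch is conditional on two-sided tests, and the CAPE-V scope point is a clarification only.

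**What to change.** 1. Delete the statement that .025 controls Type 1 error across the secondary analyses.
2. Name total VHI as the only confirmatory test, with a stated two-sided level and a matching interval: .025 with a 97.5% interval, or .05 with a 95% interval. Either is valid.
3. Present the other secondary outcomes, including the VTD items, as estimates with intervals labelled unadjusted and without significance claims. Alternatively, adjust them as a named family, for example by Holm's method.
4. State that CAPE-V follows its own rule (.0125 with 98.75% intervals) and is outside the general t-test level.
5. Report Cohen's d with a confidence interval for every outcome, whatever the test result, and say which standard deviation it uses.

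The cost is SAP wording only, with no new data or patients. Fewer secondary outcomes may be called significant.

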### 7.2.1. Size of sample

As this is a proof-of-concept study the sample size of ten patients was selected arbitrarily to generate the necessary results for a power analysis for future studies.

SHORT TITLE/ACRONYM: CVT4MTD

IRAS:306954

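### Cohen's d is planned only after a significant test, so with ten patients the printed effect sizes are a selected set and overstate moderate effects

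*Combined protocol and SAP*

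**What the plan says.** The rule is in section 5, under Acoustic, EGG and MPT measures: "Any significant treatment effects will be followed up with calculations of effect size", using Cohen's d. The same paragraph sets the threshold: "the alpha level for all t-test comparisons will also be assessed at .025". The subsections on VHI, CAPE-V and the other questionnaires mention no effect size, so nothing in the plan produces a d for an outcome that misses significance. The plan does not say whether d is standardised by the SD of the change or by a pre- or post-treatment SD, and it does not state whether tests are one- or two-sided.

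Three other places bear on the point:

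- Section 7.2.1 says the sample of ten was "selected arbitrarily to generate the necessary results for a power analysis for future studies".
- Section 4.2 lists as the fifth secondary outcome: "Review of qualitative and quantitative results with recommendations on the feasibility and design of performing a larger RCT".
- The sentence before the Cohen's d rule plans a forest plot showing the average "change for each outcome measure and corresponding 95% confidence interval". This has no significance filter.

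For CAPE-V the intervals follow a different convention: "so the reported 95% confidence interval (CI) will actually be a 98.75% CI".

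**The concern.** The study's stated product is information for planning. A planner needs an estimate and its precision for each candidate outcome, whether or not p crosses a line. Secondary objective 4 (section 4.1) also asks which measures best reflect improvement, and outcomes cannot be compared on d if those that miss the threshold have none.

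Making significance the trigger does two things in a sample of ten. It leaves out every d below a floor that is already large. It also means that a moderate true effect gets a printed d only in samples that happened to overestimate it. Anyone who reads the printed d values as the study's effect sizes would then take away figures that are too high, with no sign of the outcomes left out.

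**Working it through.** **Inputs from the documents.** n = 10 (section 7.2.1). Paired t tests on pre and post scores, alpha .025 for all t tests, d after significance only (section 5). CAPE-V has a Bonferroni adjustment for four comparisons, 0.05/4 = .0125, which matches its 98.75% interval.

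**Assumptions.** Two-sided tests; d = mean change / SD of change; true effects from 0.5 to 2.0. The documents give no expected change, SD or pre-post correlation, and no power calculation to reproduce.

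**Step 1: smallest d that can be printed.** Since t = d × √n, the floor is t(1−α/2, 9 df)/√10.

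- α = .05: 2.262/3.162 = 0.715
- α = .025: 2.685/3.162 = 0.849
- α = .0125 (CAPE-V): 3.111/3.162 = 0.984

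**Step 2: effect of the filter at .025.** The share printed is the power from the noncentral t. The unfiltered mean of d is the true value divided by the small-sample factor J = Γ(4.5)/(√4.5 × Γ(4)) = 0.914. The filtered mean is the mean of d over significant positive results.

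| True d | Share given a d | Mean printed d | Mean unfiltered d | Added by filter |
|---|---|---|---|---|
| 0.5 | 19% | 1.13 | 0.55 | 0.58 |
| 0.8 | 47% | 1.22 | 0.88 | 0.34 |
| 1.0 | 68% | 1.31 | 1.09 | 0.22 |
| 1.2 | 84% | 1.43 | 1.31 | 0.12 |
| 1.5 | 96% | 1.68 | 1.64 | 0.03 |
| 2.0 | 99.9% | 2.19 | 2.19 | 0.00 |

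The last column is taken before rounding. The gap between the unfiltered mean and the true value is ordinary small-sample bias, which the factor J removes.

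**Step 3: other readings.**

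- At two-sided .05 the mean printed d is 1.01, 1.12, 1.23, 1.38 and 1.65 for true 0.5, 0.8, 1.0, 1.2 and 1.5.
- With eight completers at .025 the floor is 1.005. At true 0.5, 14% of outcomes get a d, averaging 1.34.
- With a pre/post SD as denominator and equal SDs, the floor is 0.849 × √(2(1−r)): 1.00, 0.85, 0.66 and 0.54 for pre-post correlation r of 0.3, 0.5, 0.7 and 0.8. With the baseline SD as denominator, the mean printed d is about 2.0 times the truth where the change-score effect is 0.5, and about 1.4 times where it is 0.8, for r of 0.3, 0.5 and 0.7.

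**Step 4: what is dropped.** An observed d of 0.70 gives t = 0.70 × 3.162 = 2.21 and p = .054, with a 95% CI for d of −0.01 to 1.38. It would get no d at either alpha.

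**Step 5: what the forest plot recovers.** With all ten patients, the half-width of a 95% CI is 0.715 × SD of change, so d = 0.715 × mean / half-width. For CAPE-V the multiplier is 0.984, because the interval labelled 95% is really 98.75%. Using 0.715 there gives 0.715/0.984 = 0.727 of the right value, or 27% too small.

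**The case against.** The strongest reply is that the estimates are already reported without selection. The forest plot gives mean change and interval for each outcome, and d is only a unit-free restatement that can be worked back from it. No test, estimate or primary conclusion depends on d, and no section says the future power analysis will use the printed values. A larger RCT needs a between-group difference, so a single-arm pre-post d would be a poor planning input even if every one were reported. The inflation also depends on assumed true effects: nothing in the documents places VHI or any other outcome in the moderate range. The CAPE-V interval is openly described, so misreading it takes some carelessness.

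Most of this stands, and it limits the weight of the point. It does not remove it. The back-calculation asks readers to rebuild a column the authors could print, and it needs the number of completers and the true coverage of each interval. It recovers only the change-score d. If the authors use another denominator, the pre and post SDs and their correlation cannot be read from the plot. A rule that prints some effect sizes and withholds others by p-value is still selective reporting in a study whose sample was chosen to inform planning.

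**Conclusion.** The concern holds. Followed as written, the plan prints d only for significant outcomes. In ten patients that means nothing below 0.849 at .025 or 0.715 at .05, and an average overstatement from the filter alone of 0.58 at a true effect of 0.5 and 0.34 at 0.8, falling to 0.03 at 1.5. These sizes rest on two-sided testing, change-score standardisation and assumed true effects. The direction is the same under the other alphas, eight completers and the baseline-SD denominator. If true effects are very large, almost every d is printed and the filter does no harm. The weight is minor to moderate: a reporting flaw that should be fixed because it works against the stated use of the data and costs almost nothing to remove.

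**What to change.** Replace the Cohen's d sentence with wording to this effect:

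> For every quantitative outcome, regardless of significance, we will report the mean change, the SD of change, the pre and post SDs and their correlation, and a standardised effect defined as mean change divided by SD of change, with small-sample correction (factor 0.914 at 9 df) and its 95% confidence interval.

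State the true coverage of each interval in the forest plot, including CAPE-V, and the number of patients behind it. Add that the future power analysis will use the estimated SD with a clinically chosen target difference, not the observed pre-post d.

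The cost is two or three sentences in the plan and a few lines of code, with no new data. The only downside is that some reported effects will be small or imprecise.

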### Treating CVT Practitioner (t=0 to t=6)

Up to 6 sessions (45-60 mins) given online over a total of 6/52

- Medical/SLT assessment documentation available to Practitioner
- Assessment by treating Practitioner and treatment plan including goals agreed with patient
- Structured proforma documenting session goals, and % time of therapy used in each session completed at end of each session to form part of treatment record
- Observation by study SLT-VT, and/or recording of sessions
- Review of progress (log of treatment and study SLT -V observations where performed) by study SLT-V, study CVT-P and Laryngologist after 2 and 4 therapy sessions

If concerns about suitability of treatment for patient, they may exit the study after agreement between study team and patient

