## 7. SAMPLE AND RECRUITMENT

### 7.1. Eligibility Criteria

All patients who meet the inclusion/exclusion criteria and who give consent will be invited to take part. Ten consecutive patients will be recruited. All participants will have a multidisciplinary and multidimensional assessment (see Table 2) and considered for the study if they have a clinical diagnosis of Type I-III MTD based on consensus agreement of the patient by an SLT-V and

SHORT TITLE/ACRONYM: CVT4MTD

IRAS:306954

Laryngologist and meet the study criteria. No participants will be excluded based on race, ethnicity, or gender.

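### Cohen's d is specified without a small-sample correction or a named standardiser for at most ten pairs; averaged over all results it runs about 9% high (SD of change), and the significance filter adds a larger bias

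*Combined protocol and SAP*

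**What the plan says.** The sample is fixed in section 7.1: "Ten consecutive patients will be recruited". Section 7.2.1 explains the number: "the sample size of ten patients was selected arbitrarily to generate the necessary results for a power analysis for future studies". Section 4.2 lists as a further output: "Review of qualitative and quantitative results with recommendations on the feasibility and design of performing a larger RCT".

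For the primary outcome, section 5 (VHI) states: "Paired-samples t tests will be applied to the pre-treatment and post-treatment primary outcome measure scores (total VHI score"). The acoustic, EGG and MPT measures are tested in the same way, and "the alpha level for all t-test comparisons will also be assessed at .025". Change scores are to be shown in a forest plot "in order to display the average" change with a 95% confidence interval for each outcome. That display does not depend on significance. The effect size does: "Any significant treatment effects will be followed up with calculations of effect size using Cohen"'s d.

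The plan gives no small-sample correction and does not name the standardiser (SD of change, baseline SD, or an SD pooled over the two visits). Pairs may be lost: where there are concerns about suitability, the flow chart says of patients that "they may exit the study after agreement between study team and patient". No dropout rate is given.

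**The concern.** A standardised change divides a mean by an estimated SD. When that SD rests on nine degrees of freedom or fewer, the ratio is biased away from zero, because the reciprocal of a noisy SD is on average too large. This is a property of the estimator at this sample size, and it would remain if d were reported for every outcome.

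The plan then adds a second, distinct bias: d is calculated only when the test is significant. In a study of ten patients, only large observed changes pass that test.

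Both matter because the study's stated purpose is to supply results for a later power analysis. Cohen's d is the only standardised effect that the plan names for these comparisons, so a later team could well pick it up.

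**Working it through.** The documents state no effect size, SD or power, so there is no figure of the plan's own to reproduce.

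**Inputs.** From the documents: ten pairs (section 7.1), paired t tests and alpha .025 (section 5). Assumed: two-sided testing, normally distributed changes, 8 to 10 completers, and true standardised changes of 0.5 to 1.5.

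**Step 1: bias averaged over all results.** With d = mean change / SD of change and df = n − 1, E[d] = true value / J(df), where J(df) = Γ(df/2) / [√(df/2) · Γ((df − 1)/2)].

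- 10 pairs: J(9) = 0.9139; 1/0.9139 − 1 = 9.4%.
- 9 pairs: J(8) = 0.9027; 10.8%.
- 8 pairs: J(7) = 0.8882; 12.6%.

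A true 0.80 therefore averages 0.80/0.9139 = 0.875. The usual approximation 1 − 3/(4·df − 1) gives 1 − 3/35 = 0.914 at df = 9, which is accurate enough.

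**Step 2: dependence on the standardiser.** The baseline SD also has nine degrees of freedom and gives the same 9.4%. With the average of the pre and post variances, simulation gives 4.4% at a pre/post correlation of 0, rising to 8.2% at a correlation of 0.9.

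**Step 3: the significance filter.** With ten pairs the critical t is 2.685, so the smallest |d| that can be reported is 2.685/√10 = 0.85 (0.78 after Hedges' correction). With eight pairs it is 2.841/√8 = 1.00. Simulation of 1,000,000 paired tests per row, n = 10, two-sided alpha .025:

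| True value | Power | Mean d, all results | Mean d, significant | Mean g, significant | Mean d, not significant |
|---|---|---|---|---|---|
| 0.5 | 0.191 | 0.547 | 1.129 (+126%) | 1.032 (+106%) | 0.410 (−18%) |
| 0.8 | 0.475 | 0.875 | 1.220 (+53%) | 1.115 (+39%) | 0.564 (−30%) |
| 1.0 | 0.682 | 1.094 | 1.310 (+31%) | 1.197 (+20%) | 0.632 (−37%) |
| 1.5 | 0.964 | 1.641 | 1.676 (+12%) | 1.532 (+2%) | 0.731 (−51%) |

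The two steps agree. For a true 0.80, 0.475 × 1.220 + 0.525 × 0.564 = 0.876, which matches the 0.875 of step 1 within rounding. The 9.4% is thus a mixture of a large overstatement and an understatement.

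**Step 4: what the correction achieves.** Over all results, g is unbiased (mean 0.800 for a true 0.80), and the root mean squared error falls from about 0.44 to 0.39. Among significant results, the excess for a true 0.80 falls only from 0.420 to 0.315, so three quarters of it remains. At a true 1.5 it falls from 0.176 to 0.032.

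**The case against.** Four points can fairly be made against this concern.

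- **The bias is small against the noise.** For a true 0.80 and ten pairs, d has a standard deviation of about 0.43, so a bias of 0.075 is about 0.17 of a standard deviation. In median terms the uncorrected value is nearer the truth (median d 0.825, median g 0.754). This stands and is the main reason for rating the point minor. It does not favour d overall, since g has the smaller mean squared error.
- **A later planner need not use d.** Mean changes with 95% confidence intervals are shown for every outcome, and the SD of change can be recovered from the interval and n. This stands and limits the harm.
- **No test or decision rule uses d.** This also stands: the choice affects reporting only.
- **The 9% depends on a choice that the plan does not make.** Correct, and that is itself a reason to edit the sentence.

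A reader might also infer more than the documents support. One inference is that the 9% applies equally to significant and non-significant results; the table shows that it is the bias in neither group. Another is that Hedges' correction by itself would make the reported effect sizes unbiased; it would not while the filter stands. A third is that a future trial will be undersized by a calculable amount. The plan does not say that d will be the input to the power analysis, and a single-arm pre/post change is not a between-arm effect: there is no control arm, entry requires a VHI of at least 30, and every patient also receives indirect voice therapy. Putting this d into a two-arm formula would be invalid even after correction.

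**Conclusion.** The point holds in a limited form. Uncorrected Cohen's d from at most ten pairs overstates the true standardised change by about 9% averaged over all results if the SD of change or the baseline SD is the standardiser, by about 13% with eight pairs, and by roughly 4% to 8% with a pooled pre/post SD. These figures assume normally distributed changes.

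Calculating d only after significance does more damage. With ten pairs and two-sided alpha .025, the overstatement in what is reported runs from 12% (true 1.5) to 126% (true 0.5), and Hedges' correction leaves 2% to 106%. The plan does not state whether tests are one- or two-sided; a looser threshold would make the filter milder (at two-sided .05 the smallest reportable |d| is 0.72 instead of 0.85).

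Severity is minor: a cheap improvement to a stated estimator, with no effect on any test or interval in the plan.

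**What to change.** Replace the effect-size sentence in section 5 (Acoustic, EGG and MPT measures) with one that does three things:

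1. Names the standardiser. The SD of change or the baseline SD is simplest, because its degrees of freedom are the number of pairs minus one. For a pooled pre/post SD the effective degrees of freedom depend on the pre/post correlation.
2. Uses Hedges' g in place of Cohen's d: multiply by 1 − 3/(4·df − 1), with df from the pairs actually analysed (0.914 for ten pairs on the SD of change).
3. Reports g with a confidence interval for every outcome, regardless of significance.

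The third part is essential, since the correction alone leaves most of the selection bias unless the true effect is very large. Where results feed the later power analysis, quote g with its interval and state that it is a single-arm pre/post quantity.

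The cost is one sentence in the plan and one multiplication per outcome. No extra data are needed and study conduct does not change. Each effect size becomes up to about 9% less favourable with ten pairs, and slightly more than that if pairs are lost.
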